6.3 Imaging Core Laboratories

An independent core laboratory will be used in this study to assess the arteriograms/venograms, and DUS imaging submitted by the sites.

7 ADVERSE EVENTS

To comply with worldwide standards and guidelines on clinical investigation adverse event reporting, the Sponsor has adopted uniform and worldwide applicable standard definitions and reporting timelines to be used and adhered to by the investigators.

7.1 Definition

7.1.1 Adverse Event

An adverse event (AE) is any untoward medical occurrence, unintended disease or injury, or untoward clinical signs (including abnormal laboratory findings) in subjects, users or other persons, whether or not related to the medical device under investigation.

As part of ISO14155 Section 3.2, the Adverse Event definition has the following notes:

Note 1: This definition includes events related to the medical device under investigation or the comparator.

Note 2: This definition includes events related to the procedures involved.

Note 3: For users or other persons, this definition is restricted to events related to medical devices under investigation.

7.1.2 Serious Adverse Event

If the AE meets any of the criteria below, it is regarded as a serious adverse event (SAE).

- Led to a death,
- Led to a serious deterioration in health of the subject, that either resulted in
 - a life-threatening illness or injury, or
 - a permanent impairment of a body structure or a body function, or
 - in-patient hospitalization or prolongation of existing hospitalization, or
 - medical or surgical intervention to prevent life threatening illness or injury or permanent impairment to a body structure or a body function.
 - chronic disease
- Led to fetal distress, fetal death or a congenital abnormality or birth defect.

Note: A planned hospitalization for a pre-existing condition, or a procedure required by the CIP without a serious deterioration in health, is not considered to be an SAE.

7.1.3 Device Deficiency/Device Malfunction

Device deficiency is defined as an inadequacy of a medical device related to its identity, quality, durability, reliability, safety or performance, such as malfunction, misuse or use error and inadequate labeling. This includes the failure of the device to meet its performance specifications or otherwise perform as intended. Note: performance specifications include all claims made in the labeling of the device.

A device malfunction is the failure of a device to meet its performance specifications or otherwise perform as intended, when used in accordance with the instructions for use or CIP.

7.2 Device Relationship

Determination of whether there is a reasonable possibility that the JETi System caused or contributed to an AE is to be **determined by the Investigator** and recorded on the appropriate case report (CRF) form. Determination should be based on the assessment of temporal relationships, evidence of alternative etiology, medical/biologic plausibility and patient condition (pre-existing condition).

7.3 Adverse Event and Device Deficiency/Device Malfunction Reporting

7.3.1 Adverse Event Reporting

Safety surveillance and reporting starts as soon as the JETi catheter is introduced into the intended vasculature during the procedure. Safety surveillance and reporting will continue until sites perform the last follow-up visit, the subject is deceased, the subject concludes participation in the clinical investigation, or the subject withdraws from the clinical investigation. Sites will collect all adverse event data, including deaths and device deficiency data (if applicable), throughout the period defined above, and will report these events to the Sponsor on a CRF. Sites should update additional information regarding an adverse event on the appropriate CRF.

Unchanged, chronic, non-worsening or pre-existing conditions are not AEs and should not be reported.

The Sponsor will provide an offline form to allow the investigator to report SAEs in the event the entry cannot be made in the electronic data capture (EDC). This does not replace the EDC reporting system. Sites must still enter all information in the EDC system as soon as feasible.

For the purposes of this study, the following adverse events will be reported for each subject through the 30-day follow-up visit.

- All device-and procedure-related AEs
- All SAEs

In addition, the following adverse events regardless of seriousness or relatedness will be collected:

[REDACTED]
[REDACTED]
[REDACTED]
[REDACTED]
[REDACTED]
[REDACTED]
[REDACTED]
[REDACTED]

SAE Reporting

The investigator must report all SAEs to the Sponsor as soon as possible but no later than outlined below.

Clinical Site	Reporting timelines
All Sites	Sites must report SAEs to the Sponsor no later than 3 calendar days from the day the site personnel became aware of the event or as per the investigative site's local requirements, if the requirement is more stringent than those outlined.

Sites must record the date the site staff became aware that the event met the criteria of an SAE in the source document. The Investigator will further report the SAE to the local IRB/EC according to the institution's IRB/EC reporting requirements.

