3.1 Clinical Investigation Procedures and Follow-up Schedule

The study flowchart is shown in **Figure 1**, and the follow-up requirements are described in this section. After meeting all eligibility criteria, a subject is considered enrolled in the study from the moment the subject provides written informed consent. The point of registration in the study is when a JETi Catheter is introduced into the intended vasculature of an enrolled subject during the procedure (Day 0).

A subject who is enrolled but not registered in this study will be considered a screen failure. Consenting after the JETi procedure is deemed acceptable if all assessments needed for primary endpoints were completed at baseline. In the cases of retrospective consent, the point of registration will be the same and any procedural information would be entered post-consent and defined adverse events (AEs) will be collected retrospectively from the point of registration. All registered subjects will be followed for up to 30 days in cases of prospective consent and will vary for retrospective consent. Registered subjects will be evaluated, and data will be collected at baseline, procedure, discharge, and at 30 days after Day 0.

[figure not shown]
Figure 1: Study Flowchart

a) Prospective consent

* ≠ procedure performed in the treatment of patients undergoing a percutaneous thrombectomy procedure for peripheral arterial, venous, and arteriovenous thrombosis

b) Retrospective consent*

* procedure performed in the treatment of patients undergoing a percutaneous thrombectomy procedure for peripheral arterial, venous, and arteriovenous thrombosis

*Consenting after the index procedure is acceptable if all assessments needed for primary endpoints are complete

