4.2 Descriptive Endpoints

4.2.1 All subjects

- Procedure-related death as adjudicated by a CEC.
- JETi-related AEs collected during JETi procedure, at discharge, and 30-day follow-up, as adjudicated by a CEC.
- Procedure-related access site complications such as hematoma, pseudoaneurysm (false aneurysm), perforation, as adjudicated by a CEC.
- **Treatment Used:** The number and percentage of patients having each of the following treatments:
 - JETi mechanical thrombectomy (MT) only
 - JETi in combination with one or more of the following treatments:

- **Short-Form Health Survey-12 (SF-12)** – score at baseline and 30-day visit.

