6 TREATMENT AND EVALUATION OF ENDPOINTS

For this study, the following definitions apply:

- **Index procedure:** the entire intervention to treat the subject's peripheral vascular thrombosis. A subject's procedure may include more than one session if the subject is removed from the interventional suite and placed in a holding area with the intention of returning to the suite for additional treatments either the same day or following day (e.g., catheter placement or removal for CDT).
- **Treatment:** the individual techniques performed during a procedure to address the subject's peripheral vascular thrombosis (e.g., JETi thrombectomy, balloon angioplasty, stent placement, or catheter-directed thrombolysis (CDT)). Note that "JETi treatment" will refer to treatment during which the JETi Thrombectomy system is used.

NOTE: A subject's treatment is determined by the treating physician based on the clinical situation and institutional practices.

- **Session:** a session is the in and out period within an interventional suite that a subject is receiving treatment. A subject's procedure may include more than one session if the subject is removed from the interventional suite and placed in a holding area with the intention of returning to the suite for additional treatments either the same day or following day (e.g., catheter placement or removal for CDT).

NOTE: Treatment for unexpected re-thrombosis is an adverse event and should not be considered as an additional session of the initial procedure. Refer to **Section 7.1.1**.

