Anticoagulants, and antiplatelet medications will be collected for this study at Baseline (medications that the patient was taking within the 30 days prior to admission and upon admission), Index Procedure, Discharge, and 30-day follow-up timepoint. Thrombolytics used during the index procedure will be collected.

AEs experienced by the patient during the study will be reported, starting as soon as the JETi catheter is introduced into the intended vasculature during the procedure. Please refer to AE reporting section 7.3.1 for additional details of event reporting.

The schedule of events for arterial subjects is located in **Section 6.1.6**

Data collection at each timepoint is discussed in the sections below.

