The Short Form (SF-12) is a self-reported outcome quality of life measure. Its completion is required at baseline, and 30 days. For post-procedurally consented subject, a baseline SF-12 will not be collected as the validity of this assessment is not supported when collected retrospectively.

Anticoagulants, antiplatelet, and thrombolytic medications will be collected for this Study at Baseline (medications that the patient was taking within the 30 days prior to admission and upon admission), Index Procedure, Discharge, and 30-day follow-up timepoint. Thrombolytics used during the index procedure will be collected.

AEs experienced by the patient during the procedure through discharge will be assessed by the physician to determine if related to any portion of the procedure. If the event has been determined to be

⁶ Lattimer CR, Kalodiki E, Azzam M, Geroulakos G. Validation of the Villalta scale in assessing post-thrombotic syndrome using clinical, duplex, and hemodynamic comparators. *J Vasc Surg Venous Lymphat Disord*. 2014;2(1):8-14.
doi:10.1016/j.jvsv.2013.06.003

related to the procedure, then a determination of relatedness to the JETi System is required. All events determined by the physician to be related to the JETi System will need to be assessed as to whether the event caused serious injury or death, and will be collected.

The schedule of events for venous subjects is located in **Section 6.2.6**.

Data collection at each timepoint is discussed in the sections below.

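### Adverse-event reporting opens at JETi catheter introduction, after vascular access, so an access-site complication that arises earlier and does not worsen falls outside the required window for an endpoint meant to count it

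*Combined protocol and SAP*

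**What the plan says.** All references are to the combined protocol and SAP.

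- **Start of reporting, general rule (7.3.1):** "Safety surveillance and reporting starts as soon as the JETi catheter is introduced into the intended vasculature during the procedure". Within that window, sites report all device- and procedure-related adverse events and all serious ones. Unchanged or pre-existing conditions are not to be reported.
- **Arterial and arteriovenous subjects (6.1):** reporting is described as "starting as soon as the JETi catheter is introduced into the intended vasculature during the procedure".
- **Retrospective consent (3.1):** "defined adverse events (AEs) will be collected retrospectively from the point of registration". Registration is the moment of JETi catheter introduction (Day 0).
- **Venous subjects (6.2):** "AEs experienced by the patient during the procedure through discharge will be assessed by the physician", to decide whether they relate to any part of the procedure. No catheter-introduction start is given. The section then narrows: "All events determined by the physician to be related to the JETi System will need to be assessed" for seriousness, and it is these events that are to be collected.
- **Endpoint (4.2.1, all subjects):** "Procedure-related access site complications such as hematoma, pseudoaneurysm (false aneurysm), perforation, as adjudicated by a CEC".
- **Index procedure (6):** "the entire intervention to treat the subject's peripheral vascular thrombosis". It may comprise more than one session within two calendar days, with placement or removal of a lysis catheter as the example.

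**The concern.** The endpoint attributes access-site complications to the procedure, not to the device. The procedure is the whole intervention. The reporting window is tied to the device, and it opens after the step that causes access-site complications. A hematoma or perforation that occurs at puncture, and is stable when the JETi catheter enters, is procedure-related in the ordinary sense but arises before the window opens. A site could also read it as pre-existing at that point and, following 7.3.1, leave it out.

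The separate venous wording adds a second problem. One all-subject endpoint could be collected under different rules depending on which vessel was treated, and on whether the site follows 6.2 or 7.3.1.

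At stake are the access-site complication rate and the count of procedure-related adverse events. Section 4 makes every endpoint descriptive, with no hypothesis testing, so complete counts are what the study delivers.

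**Working it through.** The plan states no figure to reproduce: section 8.3 gives about 20 subjects without a calculation, and no access-site rate is shown. The check is first a comparison of the rules, then an illustration of size.

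**1. Order of events against the window**

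| Onset and course of an access-site complication | Within the 4.2.1 endpoint and section 6 procedure? | Inside the 7.3.1 / 6.1 / 3.1 window? |
|---|---|---|
| After access, before JETi introduction, unchanged afterwards | Yes | No |
| Before JETi introduction, worsens afterwards | Yes | Yes, as a worsening condition |
| Appears after JETi introduction | Yes | Yes |
| Patient never receives the JETi catheter | Not applicable: screen failure (3.1, 5.5) | No |

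Only the first row is lost. Since the window omits events and adds none, the reported rate can be too low but not too high.

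**2. Venous rule against the general rule**

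For assessment, 6.2 covers the procedure through discharge, which is wider at the start than 7.3.1. For collection, it commits only to JETi-related events, which is narrower than the procedure-related events that 7.3.1 requires. An access-site hematoma caused by the puncture and not by JETi would be assessed under 6.2 but not committed to collection. So 6.2 does not close the gap.

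**3. Size of one missed subject**

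Inputs: N = 20 (8.3), all registered subjects analyzed (8.1). Assumption: the rate is per subject, and the missed complication is that subject's only one.

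- Change in rate: 1/20 = 0.05, or 5 percentage points. The denominator does not change, because the subject is still registered.
- True count 1/20: 5.0%, exact (Clopper-Pearson) 95% interval 0.1% to 24.9%.
- Reported count 0/20: 0%, exact 95% interval 0% to 16.8%. The upper limit is 1 − 0.025^(1/20) = 0.168.

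**4. Chance that it happens at all**

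The documents give no risk of a complication before JETi introduction, so p below is assumed. Chance of at least one among 20 = 1 − (1 − p)^20; expected number = 20p.

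| Assumed p per subject | Expected number missed | Chance of at least one |
|---|---|---|
| 1% | 0.2 | 18% |
| 2% | 0.4 | 33% |
| 5% | 1 | 64% |
| 10% | 2 | 88% |

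These figures show sensitivity to p. They do not estimate what will occur.

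**The case against.** The strongest defense is that the start point is a coherent choice. The objective in 2.1 is the safety of the JETi System. Registration, Day 0, the analysis population and the start of adverse-event reporting share one anchor. The primary composites in 4.1 require JETi-relatedness, so events before the device enters would hardly count there. With 20 subjects, the intervals for 0/20 and 1/20 overlap heavily. All this stands, and it limits the importance of the point. It does not explain why an endpoint attributed to the procedure should use a device-based window.

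Three stronger readings are tempting and are not supported:

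- **That such complications are never counted.** Those that appear or worsen after JETi introduction are inside the window. Section 10.7 also lets safety personnel identify events for the events committee, under a charter not included here. Part of the event list in 7.3.1 is redacted and cannot be judged either way.
- **That a whole overnight lysis session is routinely lost.** Section 6 allows sessions "either the same day or following day (e.g., catheter placement or removal for CDT"), but does not place lysis before JETi. The introduction describes lysis following JETi in a cited series, and the imaging plan treats the pre-JETi image as showing initial clot burden. An earlier session is permitted, not described.
- **That the primary safety result is biased.** Its JETi-relatedness requirement leaves it essentially unaffected.

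It can also be said that the plan defines no general category of procedure-related adverse event; Appendix II addresses this for deaths only. That is correct, and it is a further reason to state the window explicitly.

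**Conclusion.** The inconsistency is real and narrow. Under 7.3.1, 6.1 and 3.1, an access-site complication that arises between vascular access and JETi introduction and does not worsen is outside the required reporting window, although 4.2.1 read with section 6 would count it. Section 6.2 does not repair this and adds a conflicting rule for venous subjects.

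The bias is downward only. It affects one descriptive endpoint and the procedure-related adverse-event count. Each subject missed is worth about 5 percentage points, assuming 20 subjects and a per-subject rate; how many would be missed is unknown. The exposed interval is usually short, and could reach into the preceding day only if an earlier session came before JETi. The conclusion rests on a literal reading of the start rule, since the case report forms and the committee charter are separate documents. It is worth correcting because the correction is cheap, not because the expected distortion is large.

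**What to change.** In 7.3.1, 6.1, 6.2 and 3.1, state one rule for arterial, arteriovenous and venous subjects alike:

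- For registered subjects, procedure-related adverse events and access-site complications are recorded from the first vascular access of the index procedure (its first session), retrospectively where needed.
- JETi catheter introduction remains Day 0, the point of registration and the start for JETi-related events.
- In 6.2, replace the commitment to JETi-related events only, so that it matches the device- and procedure-related scope of 7.3.1.

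If the sponsor prefers to keep the present window, the minimum is to say in 4.2.1 that the endpoint covers only events from JETi introduction onward, and to report it under that description. Section 6.2 would still need to be reconciled with 7.3.1.

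The cost is a few sentences of protocol text, matching case report form guidance and a few more adverse-event entries. Sections 6.1.2 and 6.2.2 already collect procedure times, access sites and the order of treatments, so little new source data is needed. The access-site rate may look slightly less favorable. One limit remains: patients who never receive the JETi catheter, including any whose access complication prevented its use, stay screen failures and are still not counted.

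### Section 7.3.1 gives two conflicting adverse event reporting scopes and 6.2 adds a third, so the CEC-adjudicated JETi-related AE rate could be understated and could differ by site or cohort

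*Combined protocol and SAP*

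**What the plan says.** All references are to the combined protocol and SAP.

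- **7.3.1, broad rule.** Surveillance starts when the catheter enters the intended vasculature. "Sites will collect all adverse event data, including deaths and device deficiency data (if applicable), throughout the period defined above". The same sentence also has sites pass what they collect on to the sponsor, using a CRF.
- **7.3.1, narrower rule.** "For the purposes of this study, the following adverse events will be reported for each subject through the 30-day follow-up visit". Two items follow: "All device-and procedure-related AEs", and all SAEs. A third group is then added: "In addition, the following adverse events regardless of seriousness or relatedness will be collected". The contents of that group are blacked out.
- **6.1, arterial and arteriovenous subjects.** "AEs experienced by the patient during the study will be reported, starting as soon as the JETi catheter is introduced", with a pointer to 7.3.1 for details.
- **6.2, venous subjects.** From the procedure through discharge, the physician first judges whether an AE is related to the procedure. Only if it is does a judgement on JETi follow. Events judged JETi-related are assessed for serious injury or death and collected.
- **3.1.** For retrospective consent, the AEs to be gathered back to registration are described only as defined ones.
- **7.2.** "Determination of whether there is a reasonable possibility that the JETi System caused or contributed to an AE is to be" decided by the investigator.
- **4.2.1.** A descriptive endpoint for all subjects: "JETi-related AEs collected during JETi procedure, at discharge, and 30-day follow-up, as adjudicated by a CEC".
- **10.7.** The CEC adjudicates pre-specified events that come from investigators or are found by safety personnel, as its charter defines.

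**The concern.** The endpoint in 4.2.1 leaves the relatedness decision to an independent committee, and 3.2 presents that committee as a safeguard against bias. The safeguard covers only events that get as far as the committee. If the site's own relatedness judgement decides whether some non-serious events are recorded at all, a wrong call of unrelated on those events is hard to correct later.

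Two things are at stake. The count of JETi-related AEs could be too low. It could also depend on which sentence of 7.3.1 a site follows, or on whether the subject is arterial or venous, so that pooled or compared figures would rest on different ascertainment. Safety is a stated objective in 2.1 and every endpoint is descriptive, so complete and uniform event capture is much of what this study can deliver.

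**Working it through.** **Step 1. Do the two rules in 7.3.1 conflict?** One way to reconcile them would be that sites collect everything but report only a subset. The text rules this out, because the broad sentence also has the collected events reported to the sponsor on a CRF. Nor can the later list be a mere illustration: if every AE were reportable, a group exempt from seriousness and relatedness conditions would have no purpose. The narrower rule therefore does restrict, and the two do not agree.

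**Step 2. Which events fall in the gap?**

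| Event as judged at the site | 7.3.1 broad | 7.3.1 narrower | 6.2 venous, through discharge |
|---|---|---|---|
| SAE, any relation | Yes | Yes | Yes, via the SAE footnote to the venous schedule |
| Non-serious, JETi-related | Yes | Yes | Yes |
| Non-serious, procedure-related, not JETi-related | Yes | Yes | Not stated |
| Non-serious, unrelated to both, on the blacked-out list | Yes | Yes | Not stated |
| Non-serious, unrelated to both, off the list | Yes | No | No |

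The last row is the gap under the narrower rule. For venous subjects before discharge, a literal reading of 6.2 may widen it to the third row.

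**Step 3. Direction.** An event that is not recorded can only be missing from the count. Any error from this source is therefore downward.

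**Step 4. Size.** The plan states no expected AE rate and no rate of disagreement between investigator and CEC, so there is no figure of its own to reproduce. The only input it gives is about 20 registered subjects (5.7 and 8.3).

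- One subject is 1/20 = 5 percentage points. This holds for a subject-level rate when the lost event was that subject's only JETi-related AE. Within a cohort the denominator is smaller and the step larger; the plan gives no cohort split.
- Exact (Clopper-Pearson) 95% intervals: 2/20 = 10% (1.2% to 31.7%); 1/20 = 5% (0.1% to 24.9%); 0/20 = 0% (0% to 16.8%).

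For illustration, let p be the true subject-level JETi-related AE rate and f the share of those events lost at the site. Both are assumed. The expected shift is −p × f, and the chance that at least one of 20 subjects is missed is 1 − (1 − p × f)^20.

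| p | f | Expected shift | Chance of at least one missed |
|---|---|---|---|
| 10% | 0% | 0 points | 0 |
| 10% | 10% | −1.0 point | 0.18 |
| 20% | 25% | −5.0 points | 0.64 |
| 30% | 50% | −15.0 points | 0.96 |

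Over p from 5% to 30% and f from 0 to 50%, the expected shift runs from 0 to −15 points. The documents do not say where in that range the study would fall.

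**The case against.** The case for leaving this as a minor wording matter has four parts.

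- **The gap is narrow.** An event must be non-serious, judged unrelated to the device, judged unrelated to the procedure, and off the list. This stands for 7.3.1. It is weaker for venous subjects, because 6.2 does not say that a procedure-related AE judged not JETi-related is collected.
- **The filter is not wholly one-way.** A reader might infer that the CEC can only move events from related to unrelated. The documents do not support that. Procedure-related AEs, all SAEs and the listed events reach the sponsor without being called JETi-related and, if adjudicated, can be upgraded.
- **There are other routes.** Section 10.7 lets safety personnel identify events, and monitoring under 10.4 includes source data verification to a planned extent. Both could recover some events. Neither is described as a systematic search for non-serious AEs missing from the CRF, and the CEC charter is not part of the documents.
- **The cross-references soften the conflict.** Section 6.1 defers to 7.3.1, so it is not an independent broad rule, and the wording in 3.1 concerns retrospective consent. Both points stand, but each leads back to the unresolved conflict in 7.3.1.

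It is also true that the endpoint is descriptive and untested, and that any primary MAE component qualifying as an SAE is reported whatever its relation. Whether a re-thrombosis, symptomatic PE or BARC 3a bleed judged non-serious and unrelated would be captured depends on the blacked-out list.

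**Conclusion.** The contradiction is real and survives these objections: 7.3.1 carries two scopes and 6.2 a third. Sites and cohorts that each follow the plan as written can produce different AE counts for the 4.2.1 endpoint.

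The consequence is conditional. The JETi-related AE rate could be understated. A reader might go further and infer that it is biased low; the documents do not show this. If sites follow the broad rule, or if no unrecorded event would have been adjudicated JETi-related, the bias is zero. A fall from 2/20 to 0/20 is likewise only an extreme case, since it needs both subjects' events to be non-serious, off the list and judged unrelated to device and procedure. What can be stated is the direction (downward, if there is any error) and the step (5 points per affected subject at N = 20). The overall size cannot be judged without the blacked-out list, the CEC charter and a disagreement rate.

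The point is worth correcting before data collection, because non-serious events that were never recorded may not be recoverable afterwards.

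**What to change.** 1. State one scope in 7.3.1. The all-AE rule it already contains is preferable: every AE from catheter introduction through the 30-day visit is entered on the CRF, whatever its seriousness or the investigator's view of relatedness.
2. Align 3.1 (retrospective consent), 6.1 and 6.2 with that scope. In 6.2, keep the physician's relatedness assessment as data to be recorded, and remove it as a condition for collection.
3. State that the CEC, or safety personnel under its charter, screens all entered AEs for JETi-relatedness whatever the investigator's judgement.
4. Leave the 3-day timelines for SAEs and device deficiencies unchanged. Do not relabel the bulleted list as expedited: those timelines do not cover non-serious related AEs, so the relabelling would create a new inconsistency.

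Deleting the broad sentence and keeping targeted collection would also remove the contradiction inside 7.3.1, but it would leave the gap in place. If the sponsor prefers that route, 6.2 still has to be aligned, and the report should say that non-serious, unlisted AEs judged unrelated at the site were not captured.

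The cost is protocol wording, plus some extra non-serious AE entries and screening over 30 days in about 20 subjects. No visits or procedures are added.
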